4.3. Secondary Endpoint Analysis

All secondary endpoints, as described in Section 1.1, will be analyzed in the evaluable population except for the safety endpoints, which will be analyzed in the safety population.

4.3.1 Main Analytical Approach

The secondary endpoints summarized at each juncture of the study are detailed in Section 4.1. The analysis approach for each secondary endpoint at each phase is as follows.

4.3.1.1 Lead-in Phase

• Testosterone at weeks 24 and 52:

ARAMON V3.0 Page: 15 of 31

The differences between the log transformed data at the visit and baseline will be estimated with 95% Confidence Intervals using SAS PROC MIXED with the ESTIMATE statement. These will be transformed to mean percent change and 95% confidence intervals using the same steps as for the primary analysis in the lead-in phase. SAS code will be similar to code shown in Appendix 5: Lead-in phase analysis for natural logarithm transformed Testosterone and other endpoints using the log transformation. Results for testosterone at week 24 and 52 will be summarized in a similar manner to the primary endpoint and depicted graphically over time with 95% confidence intervals at each visit.

• PSA responses:

o Undetectable PSA response

Undetectable PSA is defined as a baseline PSA value above the 0.2 ng/mL detection limit and a post baseline PSA level below 0.2 ng/mL, confirmed by a second subsequent PSA value below 0.2 ng/mL 3 or more weeks later, with all potential PSA values between the initial date and the confirmation date below 0.2 ng/mL.

The undetectable PSA response is defined as the number of participants with undetectable PSA divided by the total number of participants evaluable. The undetectable PSA response will be summarized at 4, 12, 24, 36 and 52 weeks.

o PSA50, PSA90

PSA50 is defined as a baseline PSA value above the 0.2 ng/mL detection limit and a post baseline \geq 50% reduction of the PSA level compared to the baseline value, confirmed by a second subsequent PSA value with a \geq 50% reduction from baseline 3 or more weeks later, with all potential PSA values between the initial date and the confirmation date showing a \geq 50% reduction from baseline. PSA90 is defined in the same way with 90% reduction.

The PSA50 response is defined as the number of participants with PSA50 divided by the total number of participants evaluable. The PSA90 response is defined the same way. PSA50 and PSA90 will be summarized at 4, 12, 24, 36 and 52 weeks.

In addition, descriptive statistics will be provided for PSA maximum percent decline of \geq 50%, \geq 90% from baseline at any time on study.

• Analysis of AEs:

All grades of the feminizing side effects of gynecomastia (including breast enlargement, breast mass, breast swelling), breast tenderness/pain, nipple pain, and hot flush will be summarized using frequencies and percentages. Incidence of AEs of special topics (Bone fractures excluding pathological fractures, Cerebral ischemia, Diabetes mellitus and Hyperglycaemia, Fall, Fatigue/ asthenic conditions, Weight decreased, Rash, Seizure, Hypertension, Vasodilatation and flushing, Mental impairment disorders, Depressed mood disorders, Breast disorders/gynecomastia, Cardiac disorders, Cerebral and intracranial hemorrhage) associated with ARI treatment will also be presented.

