1.2. Study Design

1.2.1 Overall Design

This is a two-stage open-label phase 2 study with a lead-in single-arm phase and the randomized phase, to assess the impact of androgen receptor inhibitor (ARI) darolutamide or enzalutamide as a monotherapy treatment on serum testosterone levels in men with hormone-naïve prostate cancer experiencing BCR. The study design is shown in Figure 1-1.

Figure 1-1: Overall Design

Abbreviations: ECOG Eastern cooperative oncology group, PC prostate cancer, PSADT PSA doubling time.

In the lead-in phase, participants will be treated with darolutamide (600 mg twice daily). The primary analysis of the lead-in phase will occur when the last participant in the lead-in phase has been on treatment for 12 weeks, unless the participant discontinued due to lost to follow-up, withdrawal, or death. Analysis will be based on a date-based data cut in which the cutoff date will be the last participant week 12 visit date.

The study team will review the findings from the lead-in phase and provide input on interpretation of the results from the lead-in phase. This will help guide a decision on go/no-go with the randomized phase as well as potential changes in the study design for the randomized phase by the sponsor.

In case of the decision to proceed in the randomized phase, participants will be randomized in a 1:1 ratio to receive either darolutamide (600 mg twice daily) or enzalutamide (160 mg once daily). The primary analysis of randomized phase will be conducted when the last participant in the randomized phase has been on treatment for at least 12 weeks. Similar to lead-in phase the analysis will be based on a date-based data cut.

The final analysis for both phases of the study will occur when last participant in the randomized phase has been on treatment for at least 52 weeks, unless the participant discontinued due to lost to follow-up, withdrawal, or death.

The overall sample size across the two phases is expected to be about 65 participants.

The study will comprise the following consecutive periods: Screening, Treatment, and Active Follow–up.

ARAMON V3.0 Page: 9 of 31

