1.2.1.2 Treatment period

The treatment period is defined as the time from the administration of first dose of study treatment until 52 weeks or unacceptable toxicity, withdrawal of consent, investigator's decision to stop therapy for the participant, participant decision to stop therapy, sponsor's decision to terminate the study, or death.

End of treatment (EOT) visit takes place 30 days (+7 days) after the last dose.

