4.1. General Considerations

All baseline variables will be reported using the appropriate statistics: categorical variables by frequency tables (frequencies and percentages) and continuous variables by sample statistics (i.e., mean, standard deviation, minimum, median, quartiles, and maximum). The number of participants screened will be summarized for both the lead-in and randomized cohorts.

The efficacy related endpoints will be evaluated in the evaluable population while the safety endpoints will be evaluated in the safety population.

Efficacy endpoints will consider data until last dose of study drug (while on treatment).

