4.3.1.2 Randomized Phase

• Testosterone at weeks 24 and 52:

The differences between the log transformed data at the visit and baseline will be compared across treatment groups with 95% Confidence Intervals using SAS PROC MIXED with the SLICE option and a Toeplitz covariance structure. These will be

ARAMON V3.0 Page: 16 of 31

transformed to the ratio of the fold change from baseline for darolutamide to that for enzalutamide and 95% confidence intervals using the same steps as for the primary analysis in the randomized phase. SAS code will be similar to code shown in Appendix 6: Randomized phase analysis for natural logarithm transformed Testosterone and other endpoints using the log transformation. Results will be summarized in a similar manner to the primary endpoint and will be summarized graphically using the mean percent change over time with 95% confidence intervals at each visit by treatment group, flagging visits where differences are significant at the nominal 0.05 and 0.01 levels.

• Sex hormones:

Will be analyzed at week 4, 12, 24 and 52 similar to testosterone.

• Components of fat and glucose metabolism:

Will be analyzed at week 4, 12, 24 and 52 similar to testosterone.

PSA responses

Will be compared descriptively across treatments at weeks 4, 12, 24, 36 and 52 using frequencies and percentages.

• FACT-P

Differences in the FACT-P prostate cancer subscale and total will be summarized at each visit using PROC Mixed with the SLICE option, and the mean subscale and total scores will be depicted graphically over time with 95% confidence intervals at each visit by treatment group, flagging visits where differences are significant at the nominal 0.05 and 0.01 levels. The scoring procedure for FACT-P is elaborated in Appendix 2: Scoring procedures for FACT-P.

• Analysis of AEs:

All grades of the feminizing side effects of gynecomastia (including breast enlargement, breast mass, breast swelling), breast tenderness/pain, nipple pain, and hot flush, will be summarized using frequencies and percentages by treatment group.

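### Confirmed PSA response has no scheduled on-treatment confirmation at week 52, can miss a few week-12 responses at the randomized data cut, and uses a denominator that does not match its baseline condition (minor)

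*SAP*

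**What the plan says.** **Definition.** SAP 4.3.1.1 defines undetectable PSA, PSA50 and PSA90. Each needs a baseline PSA above 0.2 ng/mL and a confirming second value; for undetectable PSA the response must be "confirmed by a second subsequent PSA value below 0.2 ng/mL 3 or more weeks later". The PSA50 rate is "the number of participants with PSA50 divided by the total number of participants evaluable", and the other two follow the same pattern. On timing, "PSA50 and PSA90 will be summarized at 4, 12, 24, 36 and 52 weeks", as is undetectable PSA. For the randomized phase, SAP 4.3.1.2 gives no separate definition: responses "Will be compared descriptively across treatments at weeks 4, 12, 24, 36 and 52 using frequencies and percentages".

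**Data window.** SAP 4.1 states: "Efficacy endpoints will consider data until last dose of study drug (while on treatment". SAP 1.2.1.2 states: "End of treatment (EOT) visit takes place 30 days (+7 days) after the last dose".

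**Data cuts.** For the lead-in primary analysis, SAP 1.2.1 says "the cutoff date will be the last participant week 12 visit date". The randomized primary analysis takes place once the last participant has at least 12 weeks of treatment, on a date-based cut described as similar. SAP 4.1.1 assigns PSA at weeks 4 and 12 to that analysis and only visits after week 12 to the final analysis.

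**Unconfirmed summaries.** SAP 4.6.1 repeats the PSA analysis without confirmation, for the lead-in primary analysis only; the version history gives as the reason that the study is still running at that time. Separately, SAP 4.3.1.1 says "descriptive statistics will be provided for PSA maximum percent decline of" at least 50% and at least 90%, at any time on study.

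**Protocol.** Sections 9.4.2.1 and 9.4.2.2 list 30%, 50% and 90% decreases, with no confirmation or baseline condition. SAP 1 and SAP 4.8 both report no changes to the protocol analyses.

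**The concern.** A confirmed-response rule works only if a confirming sample can fall inside the data window. At week 52, the last reporting time, none is scheduled on treatment. At an early cut, some men will not yet have reached the confirming visit. In both cases a genuine response is recorded as non-response. The plan already allows for the second problem at the lead-in primary analysis, but not at the randomized primary analysis, which is also taken while men are still being followed.

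The denominator adds a separate mismatch: a man whose baseline PSA is at or below 0.2 ng/mL can never enter the numerator but is still counted below the line.

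All three effects lower the reported rate. With about 17 evaluable men per arm, one man is worth 5.9 points, so small miscounts are visible in the tables. What is at stake is the accuracy of a descriptive secondary endpoint.

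**Working it through.** The documents give no PSA response rate or PSA-based sample size, so there is no plan figure to reproduce. The check is visit, accrual and denominator arithmetic.

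**1. Which visits can be confirmed?** Post-baseline PSA visits in Protocol Tables 1-3 and 1-4 are weeks 2, 4, 8, 12, 16, 24, 36, 52 and EOT. The first scheduled on-treatment PSA at least 21 days later is:

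| Response first seen at week | Confirming week | Days later |
|---|---|---|
| 2 | 8 | 42 |
| 4 | 8 | 28 |
| 8 | 12 | 28 |
| 12 | 16 | 28 |
| 16 | 24 | 56 |
| 24 | 36 | 84 |
| 36 | 52 | 112 |
| 52 | none | – |

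EOT is 30 to 37 days after last dose. That satisfies the 3-week interval but lies outside the SAP 4.1 window. It takes both rules together to leave week 52 unconfirmed.

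Reading the week-52 rate cumulatively (response at or before that visit), only first responses at week 52 are at risk. Each costs 1/20 = 5.0 points in the lead-in phase or 1/17 = 5.9 points in a randomized arm (34/2 = 17). Seven earlier on-treatment visits make this rare. Read visit by visit, the effect is larger: every confirmed week-52 response would depend on an unscheduled sample.

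**2. Randomized primary cut.** Inputs: 40 men enrolled over 12 months (Protocol 1.4.1), about 34 evaluable (Protocol 9.2.2), confirmation of week 12 at week 16. Assume uniform accrual and a cut at the last week-12 visit. The last man always lacks week 16, and those who entered in the 4 weeks before him lack it too:

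- Expected number = 1 + N × 4/52
- N = 40: 1 + 3.08 = 4.1
- N = 34: 1 + 2.62 = 3.6

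Simulation under the same assumptions gave 4.1 of 40 and 3.6 of 34. With visits spread uniformly over the ±7-day windows, and confirmation moved to week 24 when week 16 falls fewer than 21 days after week 12, it gave 4.8 of 40 (5th to 95th percentile 2 to 8) and 4.3 of 34.

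On the cumulative reading, only men whose first response is at week 12 are missed. The documents do not give that share; take 10% to 20%:

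- Low: 3.6 × 0.10 = 0.36 men; 0.36/34 = 1.1 points
- High: 4.3 × 0.20 = 0.86 men; 0.86/34 = 2.5 points

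The result scales in proportion to the assumed share.

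**3. Denominator.** SAP 4.3 puts secondary endpoints in the evaluable population, which SAP Tables 3-1 and 3-2 define by eligibility and testosterone data, with no PSA condition. Protocol 5.1 criterion 4 admits a PSA of exactly 0.2 ng/mL after prostatectomy (following adjuvant or salvage radiotherapy, or in men unfit for it). SAP 4.1.3 takes the baseline value nearest first dose, which can differ from the qualifying screening value. With k men at or below 0.2 among n, the reported rate is r × (n − k)/n. Assume r = 80%:

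- n = 20, k = 1: 0.80 × 19/20 = 76.0%
- n = 17, k = 0, 1, 2, 3: 80%, 75.3%, 70.6%, 65.9%

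The documents give no value for k.

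**4. Documentation.** The protocol lists three PSA levels. The SAP keeps 50% and 90%, drops 30% and adds undetectable PSA. The SAP version history records the 30% removal with a reason; SAP 4.8 and SAP 1 do not reflect it.

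**The case against.** The case for leaving the plan alone has several sound parts.

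- Any confirmed-response endpoint has a last visit that cannot be confirmed on schedule. A reader might infer that a week-52 response can never be confirmed. The documents do not go that far: men may continue darolutamide after week 52 (Protocol 6.8), and SAP 4.1.3 allows an unscheduled value when no scheduled one exists. What stands is that no on-treatment confirming sample is scheduled.
- The rule fixing the cut at the last week-12 visit is written for the lead-in phase. The randomized wording permits a later cut, and later data can complete the confirmation, so loss of week-12 responses is possible rather than certain. But SAP 4.1.1 does not say that the week-12 rate is reported again at the final analysis.
- The unconfirmed maximum-decline summary would capture these men for the 50% and 90% levels. It has no counterpart for PSA below 0.2 ng/mL.
- Keeping all evaluable men in the denominator is a defensible conservative convention, and it applies equally to both arms. Entry requires PSA of at least 0.2 ng/mL and a doubling time of 20 months or less, so men at or below 0.2 at baseline are probably few.
- A reader might take the missing entry in SAP 4.8 for a concealed change. It is not: the version history of the same SAP states it openly.

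**Conclusion.** The point holds as a minor one. The confirmation rule and the on-treatment window together leave week 52 without a scheduled confirming PSA. The randomized primary analysis lacks the non-confirmed repeat that the lead-in primary analysis has. The numerator and denominator apply different baseline conditions.

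Expected sizes are small: rare single men at week 52, and 1.1 to 2.5 points at the randomized week-12 cut. The latter rests on uniform accrual, a cut at the last week-12 visit, the cumulative reading and an assumed 10% to 20% first responding at week 12. The denominator effect is nil if no man has baseline PSA at or below 0.2 ng/mL. The 30% level is a documentation matter only.

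A reader might infer that the trial's main conclusions are at risk. They are not: PSA response is secondary and descriptive, and the primary test, its alpha and power, and the testosterone condition for opening the randomized phase do not use it.

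**What to change.** Two changes to the analysis:

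1. Extend the non-confirmed PSA50, PSA90 and PSA below 0.2 ng/mL summaries of SAP 4.6.1 to the randomized primary analysis and to the final analysis of both phases, shown beside the confirmed rates.
2. Restrict each PSA response denominator to evaluable participants with baseline PSA above 0.2 ng/mL.

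Three clarifications in the text:

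- say whether the rates are cumulative or by visit;
- say that the week-12 confirmed rate is reported again at the final analysis;
- list in SAP 4.8 the removal of the 30% level and the added confirmation and baseline conditions, and align SAP 1.

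The cost is SAP wording and a few table rows. Every PSA value needed is already scheduled, and the non-confirmed analysis is already planned for the lead-in phase. The downsides are that unconfirmed rates may include transient falls, which is why the confirmed rates stay beside them, and that denominators may be slightly smaller.

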4.3.1.2 Randomized Phase

• Testosterone at weeks 24 and 52:

The differences between the log transformed data at the visit and baseline will be compared across treatment groups with 95% Confidence Intervals using SAS PROC MIXED with the SLICE option and a Toeplitz covariance structure. These will be

ARAMON V3.0 Page: 16 of 31

transformed to the ratio of the fold change from baseline for darolutamide to that for enzalutamide and 95% confidence intervals using the same steps as for the primary analysis in the randomized phase. SAS code will be similar to code shown in Appendix 6: Randomized phase analysis for natural logarithm transformed Testosterone and other endpoints using the log transformation. Results will be summarized in a similar manner to the primary endpoint and will be summarized graphically using the mean percent change over time with 95% confidence intervals at each visit by treatment group, flagging visits where differences are significant at the nominal 0.05 and 0.01 levels.

• Sex hormones:

Will be analyzed at week 4, 12, 24 and 52 similar to testosterone.

• Components of fat and glucose metabolism:

Will be analyzed at week 4, 12, 24 and 52 similar to testosterone.

PSA responses

Will be compared descriptively across treatments at weeks 4, 12, 24, 36 and 52 using frequencies and percentages.

• FACT-P

Differences in the FACT-P prostate cancer subscale and total will be summarized at each visit using PROC Mixed with the SLICE option, and the mean subscale and total scores will be depicted graphically over time with 95% confidence intervals at each visit by treatment group, flagging visits where differences are significant at the nominal 0.05 and 0.01 levels. The scoring procedure for FACT-P is elaborated in Appendix 2: Scoring procedures for FACT-P.

• Analysis of AEs:

All grades of the feminizing side effects of gynecomastia (including breast enlargement, breast mass, breast swelling), breast tenderness/pain, nipple pain, and hot flush, will be summarized using frequencies and percentages by treatment group.

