9.4.2.2 Randomized Phase

For testosterone at the visits at week 24 and 52, and for each of the sex hormones, and for each of the components of fat and glucose metabolism at weeks 4, 12, 24 and 52, the differences between the log transformed data at the visit and that at baseline will be compared across treatment groups with 95% Confidence Intervals using SAS PROC MIXED with the SLICE option and a Toeplitz covariance structure. These are to be transformed to the ratio of the fold change from baseline for darolutamide to that for enzalutamide and 95% confidence intervals using the same steps as for the primary analysis in the randomized phase. Results will be analyzed in a similar manner to the primary endpoint for testosterone at week 24 and 52 and for the other sex hormones and the metabolic endpoints. These analyses will be summarized graphically using the mean percent change over time with 95% confidence intervals at each visit by treatment group, flagging visits where differences are significant at the nominal 0.05 and 0.01 levels.

Page: 61 of 86

PSA response rates will be compared descriptively across treatments at week 4, 12, 24, 36 and 52 using frequencies and percentages. Response levels to be summarized will be 30%, 50% and 90% decreases.

Differences in the FACT-P prostate cancer subscale will be summarized at each visit using PROC Mixed with the SLICE option and the mean subscale score will be depicted graphically over time with 95% confidence intervals at each visit by treatment group, flagging visits where differences are significant at the nominal 0.05 and 0.01 levels.

Feminizing side effects of gynecomastia, breast tenderness/pain, nipple pain, and hot flush will be summarized using frequencies and percentages by treatment group.

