4.4. Other Exploratory Endpoints

• Markers of bone turnover:

Will be analyzed for the randomized phase as described for the sex hormones and components of fat and glucose metabolism in Section 4.3.1.2.

• Physical function measures:

Will be summarized graphically as described for the FACT-P subscale in Section 4.3.1.2. The scoring procedures for PROMIS physical function questionnaires are elaborated in Appendix 3: Scoring for PROMIS.

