6.1.2 Demographics and baseline characteristics

Overall descriptive summaries of demographics and baseline characteristics will be presented for the lead-in phase, and by treatment arm as well for the randomized phase on the Evaluable population.

The following demographic data will be summarized:

- Age (years)
- Age category ($<65, 65-74, 75-84, \ge 85 \text{ years}$)
- Ethnicity
- Race
- Weight (kg)
- BMI (kg/m²)

The following baseline characteristics will be summarized:

- ECOG Performance Status
- Stage of prostate cancer at initial diagnosis
- Gleason score of prostate cancer (<8, \ge 8) at initial diagnosis
- Stage of prostate cancer at study entry
- Serum testosterone group ($< 150 \text{ ng/dL}, \ge 150 \text{ ng/dL}$)
- Time from initial diagnosis to first dose of study drug (months)
- Bone lesions at baseline (Y/N)
- Number of bone lesions at baseline
- Hepatic function at baseline:
 - o Normal: Total bilirubin and AST \leq upper limit of normal (ULN)

ARAMON V3.0

o Mild impairment: Total bilirubin > ULN to 1.5 x ULN or (Total bilirubin ≤ ULN and AST > ULN)

Page: 22 of 31

- o Moderate impairment: Total bilirubin > 1.5 to 3 x ULN, any AST
- Severe impairment: Total bilirubin > 3 x ULN, any AST.
- Estimated glomerular filtration rate (eGFR) at baseline:
 - o eGFR = $[(140 Age) \times Weight/(72 \times Creatinine)]$.

The following baseline lab values, assessed in secondary and exploratory endpoints, will be summarized in a separate baseline table:

- Serum testosterone
- Free testosterone
- PSA
- Sex hormones
- Fat and glucose metabolism
- FACT-P
- Bone turnover
- Physical function

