These fold changes can be converted to Percent Change as:

```
PC = (FC-1)*100;

LCL_PC = (LCL_FC -1)*100;

UCL_PC = (UCL_FC -1)*100;
```

Similar code will be used for the other endpoints using the same transformation.

Appendix 6: Randomized phase analysis for natural logarithm transformed Testosterone and other endpoints using the log transformation

The following data structure will be obtained for the input dataset LN_DATA to Proc Mixed. LN_Change will be the difference between the LN(Testosterone) values at Visit from the LN value at baseline.

```
Subjid trt
                LN Change
          visit
     Daro WK2 0.5
     Daro
          WK4 0.9
     Daro WK8 1.3
     Daro WK16 1.6
     Daro WK24 1.7
     Daro WK36 1.7
          Wk52 1.6
     Daro
     Daro WK2 0.4
     Daro WK4 1.3
     ENZA WK2 0.5
     ENZA WK4 2.2
     ENZA WK8 2.6
     ENZA WK16 2.8
```

The following PROC Mixed code will be used.

ARAMON V3.0 Page: 29 of 31

```
PROC MIXED DATA = LN_DATA;
CLASS TRT VISIT SUBJID;
MODEL LN_CHANGE = TRT|VISIT /DDFM = KR;
RANDOM SUBJID(TRT);
REPEATED / TYPE = TOEP SUBJID(TRT);
LSMEANS TRT*VISIT/ DIFF SLICE = VISIT;
RUN;
```

Output the dataset created by LSMEANS. The data will be of the form:

| Obs | Effect | Trt | Visit | _Trt | _Visit | Estimate | StdErr | DF | t-value F | Probt |
|-----|-----------|------|-------|------|--------|----------|--------|-----|-----------|-------|
| 1 | TRT*VISIT | Daro | WK2 | Daro | WK4 | 0.4 | 0.3 | XXX | XXX | 0.xx |
| 2 | TRT*VISIT | Daro | WK2 | Daro | WK8 | 0.8 | 0.32 | XXX | XXX | 0.xx |
| | | | | | | | | | | |
| | TRT*VISIT | Daro | WK2 | ENZA | WK2 | -0.2 | 0.31 | XXX | xxx | 0.xx |
| | | | | | | | | | | |
| | TRT*VISIT | Daro | WK52 | ENZA | WK52 | 0.4 | 0.3 | XXX | XXX | 0.xx |

From this dataset the records where 'Trt NE _Trt', where Trt = 'Daro', where 'Visit = _Visit' and Visit IN ('WK24','WK52") will be selected. This will select the two records where we are reporting results per the secondary objective. The fold change ratio (FCR) and the lower (LCL) and upper (UCL) confidence intervals for the fold change ratio will be obtained as:

```
FCR = EXP(Estimate);

LCL_FCR = EXP(Estimate - StdErr*quantile('T', .975, DF));

UCL_FCR = EXP(Estimate + StdErr*quantile('T', .975, DF))));
```

For fold change (FC) within treatment, the PROC MIXED will be repeated above with the following LSMEANS statement:

LSMEANS TRT*VISIT/CL;

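### The FACT-P arm comparison names no baseline term, although baseline FACT-P is collected; adding it as a covariate would sharpen the estimate at little cost

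*SAP*

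**What the plan says.** FACT-P is a secondary endpoint of the randomized phase (protocol Table 3-2, SAP Table 1-2). SAP 4.3.1.2 states: "Differences in the FACT-P prostate cancer subscale and total will be summarized at each visit using PROC Mixed with the SLICE option". Protocol 9.4.2.2 reads "Differences in the FACT-P prostate cancer subscale will be summarized at each visit using PROC Mixed with the SLICE option", so the SAP adds the total score but not a baseline term. What is plotted is the score itself: "the mean subscale and total scores will be depicted graphically over time with 95% confidence intervals at each visit by treatment group", with a rule for "flagging visits where differences are significant at the nominal 0.05 and 0.01 levels".

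The laboratory endpoints in the same SAP section are treated differently. For testosterone, "The differences between the log transformed data at the visit and baseline will be compared across treatment groups", and sex hormones and metabolic markers follow that method. The only mixed-model code for the randomized phase, SAP Appendix 6, has "MODEL LN_CHANGE = TRT|VISIT /DDFM = KR". It serves log-transformed endpoints and contains no baseline covariate, so it does not supply a FACT-P model.

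Baseline FACT-P is scheduled in protocol Table 1-4. SAP 6.1.2 lists FACT-P and physical function among the variables "assessed in secondary and exploratory endpoints, will be summarized in a separate baseline table". That is the only stated use of the baseline scores.

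The exploratory physical-function scores inherit the FACT-P display. SAP 4.4 says: "Will be summarized graphically as described for the FACT-P subscale in Section 4.3.1.2".

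**The concern.** Quality-of-life scores usually differ a good deal between men and are partly stable within a man. If so, part of the spread in a visit score was already present at baseline and can be removed by adjustment. A comparison of raw visit scores leaves it in, so the confidence interval for the arm difference is wider than it need be.

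The trial is small, and protocol 6.3 names no stratification factor, so nothing in the design balances baseline FACT-P between arms. In a raw comparison, a share of any chance baseline difference, equal to the baseline-to-visit correlation, passes into each later visit in the same direction. A baseline covariate corrects for the imbalance that actually occurred.

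At stake is how informative the randomized quality-of-life comparison is. The primary testosterone analysis is not touched.

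**Working it through.** **The plan's own figure.** The documents give no sample size, SD or power for FACT-P. The one stated figure is 85% power for testosterone with 20 per arm (SAP section 5).
- Log-scale SD = sqrt(ln(1+CV²)). Fold changes of 1.45 (SD 0.65) and 2.10 (SD 0.75) give 0.428 and 0.346.
- The log difference is ln(2.10/1.45) = 0.370.
- Power is 85.3% by the normal approximation and 83.4% by the noncentral t.

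The stated figure therefore reproduces, but it neither supports nor weakens the FACT-P point.

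**Inputs for FACT-P.**
- About 34 evaluable men (SAP section 5) at 1:1 allocation (SAP 1.2.1), taken as n = 17 per arm.
- The baseline-to-visit correlation ρ is not in the documents. It is an assumption, shown from 0 to 0.8.
- All results are in units of the score's between-man SD, assumed equal at baseline and at the visit, for one visit with complete data.

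**Formulas for the SE of the arm difference.**
- Raw score: sqrt(2/n) = sqrt(2/17) = 0.343
- Change score: 0.343 × sqrt(2 − 2ρ)
- Baseline as covariate: 0.343 × sqrt(1 − ρ²) × sqrt(1 + 1/30). The last factor is the small-sample cost of estimating the slope, with N − 4 = 30.

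The half-width is the SE times the t quantile: 2.037 on 32 df for raw and change, 2.040 on 31 df with the covariate. For example, at ρ = 0.5 the covariate SE is 0.343 × 0.866 × 1.0165 = 0.302, and 0.302 × 2.040 = 0.616.

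| ρ (assumed) | Raw | Change score | Baseline as covariate | Covariate vs raw |
|---|---|---|---|---|
| 0 | 0.70 | 0.99 | 0.71 | 2% wider |
| 0.2 | 0.70 | 0.88 | 0.70 | about equal |
| 0.3 | 0.70 | 0.83 | 0.68 | 3% narrower |
| 0.5 | 0.70 | 0.70 | 0.62 | 12% narrower |
| 0.6 | 0.70 | 0.63 | 0.57 | 19% narrower |
| 0.7 | 0.70 | 0.54 | 0.51 | 27% narrower |
| 0.8 | 0.70 | 0.44 | 0.43 | 39% narrower |

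With all 20 per arm, the raw half-width is 0.64 SD, and the covariate gives 0.62, 0.56 and 0.46 at ρ = 0.3, 0.5 and 0.7.

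For an illustrative true difference of 0.8 SD with 17 per arm, power is 62% raw. With the covariate it is 64%, 73% and 88% at ρ = 0.3, 0.5 and 0.7.

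**Chance imbalance.** The baseline arm difference also has SE 0.343 SD. The probability of at least 0.25 SD in either direction is 47%, and of at least 0.5 SD it is 15%. The shift carried into a visit is ρ times the imbalance. For a one-SE imbalance that is 0.10, 0.17 and 0.24 SD at ρ = 0.3, 0.5 and 0.7.

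**Effect on nominal flags, with no drug effect.** Given the imbalance, the raw estimate has mean ρ × imbalance and SE 0.343 × sqrt(1 − ρ²). It is flagged beyond about ±1.96 × 0.343 = ±0.672. At ρ = 0.3, 0.5 and 0.7:
- a one-SE imbalance (0.34 SD) gives flag rates of 5.0%, 4.8% and 3.8%;
- a 0.5 SD imbalance gives about 6%, 8% and 9%.

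**The case against.** The strongest reply is that randomization already protects the comparison. That stands: the raw difference is unbiased on average, and the unconditional 5% error rate at each visit holds. A reader might infer that runs of flagged visits would probably be artefacts of one baseline difference. The documents and the arithmetic do not support that. A typical, one-SE imbalance leaves the flag rate at or below 5%, and its shift of 0.10 to 0.24 SD is far short of the 0.70 SD half-width. Inflation needs a larger imbalance, and at 0.5 SD, with about a 15% chance of occurring, it is modest. The durable argument is precision.

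A second reply is that neither document says baseline is ignored. That is also fair. No FACT-P model is written, and elsewhere in SAP 4.3.1.2 the word for difference means visit minus baseline. Raw comparison remains the plainer reading, because the FACT-P text plots mean scores where the laboratory text plots percent change. Adding baseline merely as another visit would not help: in an unconstrained treatment-by-visit model with complete data, the post-baseline contrasts are still raw differences.

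Third, the gain depends on an unknown correlation and is negligible if that is low. This stands and is why the range is shown. In addition, SAP 6.1.2 would make a baseline imbalance visible, the flags are called nominal, and the trial was not sized for FACT-P. These limit the consequence; they do not recover the precision.

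**Conclusion.** The point holds as an efficiency improvement to a secondary analysis. As written, the FACT-P comparison names no baseline term and has no model statement. On the plain reading it discards information the trial collects. With 17 per arm, baseline adjustment would narrow the 95% CI by 3%, 12% or 27% at an assumed correlation of 0.3, 0.5 or 0.7. It breaks even near 0.2 and costs 2% at zero. It would also correct for the observed baseline imbalance.

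Two wider readings should be avoided. Physical function is exploratory and only summarized graphically, so a between-arm comparison arises there only through the inherited flags. Nor is a baseline survey guaranteed for every man: the footnotes to protocol Table 1-4 make the PROMIS, Self-Efficacy and Godin surveys non-mandatory where no translation exists. FACT-P is better placed, because inclusion criterion 12 requires a language validated for it.

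**What to change.** In SAP 4.3.1.2, write out the FACT-P mixed model for the subscale and total: treatment, visit, treatment-by-visit, baseline score and baseline-by-visit, with the covariance structure stated. Report the adjusted arm difference and 95% CI at each visit, base any nominal flags on it, and keep raw means by arm as descriptive.

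Do not substitute a plain change score without the covariate. At correlations below 0.5 it is less precise than the raw score (half-width 0.83 against 0.70 SD at 0.3).

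In SAP 4.4, apply the same model to the physical-function scores if the inherited flags are kept; otherwise say that those plots are descriptive and carry no flags.

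The cost is SAP wording, a written model and a few degrees of freedom. Men without a baseline score leave the adjusted model, which should affect mainly the surveys. No new data are needed.
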